## STATEMENT OF COMPLIANCE

The trial will be carried out in accordance with International Conference on Harmonisation Good Clinical Practice (ICH GCP) and the following:

- United States (US) Code of Federal Regulations (CFR) applicable to clinical studies (45 CFR Part 46, 21 CFR Part 50, 21 CFR Part 56, 21 CFR Part 312, and/or 21 CFR Part 812)

National Institutes of Health (NIH)-funded investigators and clinical trial site staff who are responsible for the conduct, management, or oversight of NIH-funded clinical trials have completed Human Subjects Protection and ICH GCP Training.

The protocol, informed consent form(s), recruitment materials, and all participant materials will be submitted to the Institutional Review Board (IRB) for review and approval. Approval of both the protocol and the consent form must be obtained before any participant is enrolled. Any amendment to the protocol will require review and approval by the IRB before the changes are implemented to the study. In addition, all changes to the consent form will be IRB-approved; a determination will be made regarding whether a new consent needs to be obtained from participants who provided consent, using a previously approved consent form.]

## 1 PROTOCOL SUMMARY

### 1.1 SYNOPSIS

Title:	Development of a Novel Transdiagnostic Intervention for Anhedonia
Study Description:	
The overall goal of this project is to develop a novel transdiagnostic treatment for anhedonia, called Behavioral Activation Treatment for Anhedonia (BATA), using ultra-high field functional neuroimaging. There is a critical need for a validated treatment that specifically targets anhedonia, and this project will evaluate the effects of this new treatment on anhedonia and will establish how this treatment impacts brain systems that mediate reward processing, clinical symptoms of anhedonia, functional outcomes, and behavioral indices of reward processing. During the first phase of the study (R61-i.e., the first 60 participants), both groups will receive pre- and post-treatment scans as well as two mid-treatment scans (weeks 8 and 12) to evaluate treatment dose (4 scans total). During the second phase of the study (R33-i.e., the remaining 150 participants), participants will receive only pre- and post-treatment scans (2 scans total). All participants will complete interview, symptom, and behavioral measures before and after treatment. PET supplement: 30 participants that are part of the main parent NIMH grant will be asked to enroll in the PET sub-study & complete up to 2 PET scans pre/post during the study. It is optional, so participants may refuse & still participate in the main study. Of the 30 enrolled in the PET sub-study, ~50% will be randomized to the investigational treatment BATA & ~50% to the control condition, MBCT.
 
R61 Phase: Aim 1: To evaluate whether BATA produces changes in neural responses to reward anticipation and reward outcomes using fMRI that exceed changes due to an active comparison treatment, specifically

Objectives:	

*Mindfulness Based Cognitive Therapy (MBCT) and does not impact neural responses to threat. This aim pertains to only the first 60 participants randomized into the study (n=30 to receive BATA and n=30 to receive MBCT). **Aim 2:** To evaluate relations between BATA dose (treatment duration) and neural target engagement by examining changes in neural response to rewards with mid-treatment fMRI scans 8 and 12 weeks after starting the 15-week treatment.*

*R33 phase of this grant, pertains up to 210 participants in the study (105 randomized to BATA & 105 randomized to MBCT):*

***Aim 3:** To evaluate the effects of BATA versus an active comparison treatment on anhedonic symptoms and functional outcomes.*

***Aim 4:** To evaluate the effects of BATA versus an active comparison treatment on behavioral indices of reward sensitivity.*

***Aim 5:** To evaluate the effects of BATA versus a comparison treatment on neural response to rewards.*

**PET & EMA sub-study Aims:**

**Aim 1 (PET):** To evaluate the effects of BATA, relative to a comparison treatment, on PET-derived measures of DA functioning during incentive processing. We hypothesize that BATA, but not the comparison treatment, will result in increased phasic striatal DA release but will not influence background DA striatal tone. **Aim 2 (PET):** To evaluate relations between treatment-related changes in fMRI-derived mesocorticolimbic activation and PET-derived DA functioning in the BATA-treated group. We hypothesize that normalization of fMRI-derived mesocorticolimbic activation due to BATA specifically will be associated with increased phasic DA release but no change in background DA tone during incentive processing. **Aim 3 (EMA):** To evaluate if BATA, relative to a comparison treatment, produces improvements in real-world positive affect and the use of BATA skills. **Aim 4 (EMA):** To evaluate relations between treatment-related changes in fMRI-derived mesocorticolimbic activation and real-world positive affect and the use of relevant BATA skills.

**Endpoints:**

*Primary Endpoints:*

*Imaging (7T) – Tasking based activation to Monetary Incentive Delay (MID) Task; Task based activation to Emotion Reactivity task (Hammer)  
Behavioral/Observational:-Probabilistic Reward Task (PRT) and EffortExpenditure for Reward Task (EEfRT); Changes in SHAPs scores pre/post treatment*

*Secondary & Exploratory Endpoints:*

*Imaging (7T)- Resting state connectivity  
Behavioral/Observational -CGI-I; Homework Completion (participation and clinician-rated); ecological momentary assessment of activation, mood, reward experiences. Passive location tracking (PLT) data via the MetricWire app for the EMA sub-study to compare distance traveled before and after both treatments as a secondary, exploratory measure of behavioral activation. Follow-up analyses will evaluate relations between motion tracking, behavioral, brain, and clinical measures of response to both treatments.*

*PET Aim1: Extract dynamic change in binding potential (BPND%) before, during and after the task and then comparing these values before and after treatment between treatment groups. PET Aim2: Correlations between changes in PET striatal binding potential magnitudes and changes in fMRI.*

Study Population:	This study will recruit participants with clinically significant anhedonia, who are 18-50 years old who are able to read & understand English, and who are seeking treatment.
Phase:	Phase I/II
Description of Sites/Facilities Enrolling Participants:	Recruitment and therapeutic intervention for the study managed by Duke University Medical Center, Department of Psychiatry and Behavioral Sciences and Duke PI ;Eligible participants based on the initial Duke study assessment consent at UNC-Chapel Hill in the Department of Psychiatry under UNC PI for all 7T imaging, EMA and optional PET Scans.
Description of Study Intervention:	BATA: modified Behavioral Activation Treatment for Depression to create Behavioral Activation Treatment for Anhedonia (BATA). Treatment in the R61 phase (Phase I) will consist of up to 15 weekly 45-minute sessions. In the R33 phase, BATA sessions will again be from 8 to 15 weekly 45-minute sessions. BATA will be compared to MBCT (Mindfulness-Based Cognitive Therapy), chosen because its mechanisms of action are hypothesized to impact different brain mechanisms than BATA. To control for nonspecific factors in BATA including clinician contact, MBCT is administered in an individual format. MBCT in the R61 phase will be compromised of up to 15 weekly 45-minute sessions. In the R33 phase, the number of sessions match that of BATA.
Study Duration:	72 months
Participant Duration:	Three to five months

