## 9 STATISTICAL CONSIDERATIONS

### 9.1 SAMPLE SIZE DETERMINATION

**Aims 1, 2, and 5:** To evaluate whether BATA produces changes in neural responses to reward anticipation and reward outcomes that (1) exceed our *a priori* target engagement criteria; (2) exceed changes due to a comparison treatment; and (3) does not impact neural responses to threat. To evaluate relations between BATA dose and neural target engagement by examining changes in reward responding with fMRI scans 8, 12 and 16 weeks after starting the 15-week treatment.

Power is calculated for Aim 1 fMRI analyses because of its smaller sample, and the Aims that involve all 210 participants will have higher power because of the larger sample and optimized BATA dose. For Aim 1 we will enroll 30 outpatients per group to have complete data from 25 per group. Based on our pilot data demonstrating increased right CN activation during reward anticipation and decreased rACC activation during reward outcomes, we calculated an effect size of approximately  $z=4.1$ . Conservatively, we estimate the effect size for the increased right CN activation and reduced rACC activation will be in the range of  $z = (0.75-1.25)$ . Our models will thus have  $>90\%$  power at  $\alpha=0.025$ .

**Aims 3 and 4:** To evaluate the effects of BATA versus MBCT on anhedonic symptoms, functional outcomes, and behavioral indices of reward sensitivity. Our power analysis addresses the effects of BATA versus MBCT on SHAPS scores (conducted with Gpower) as an ANCOVA with two groups and two timepoints. With 65 subjects per treatment group with complete data at post-treatment,  $\alpha = .05$ , and assumed correlation between assessments of 0.35 (based on preliminary studies), we will have 98% power to detect small ( $f = .2$ ) effects. Pilot data in depressed patients indicated a large effect from pre-to post-treatment ( $d=1.24$ ,  $f = .62$ ), and we are powered to detect these effects. We are 80% powered to detect the interactions with effects as small as  $f = .14$ .

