**Aim 2:** We will analyze whether dose moderates treatment response via regression models that predict change in neural target (CN and dACC) activation from the number of sessions as an indicator of BATA dose. Hierarchical linear modeling where time-in-weeks is treated as a continuous variable nested within subject will provide parameter estimates of the linear, quadratic, and cubic functions for change over time in neural target engagement over the course of treatment. Standard evaluation (e.g., significant at  $p < .05$ ) will guide our selection of the most appropriate function. From these functions, we can estimate both the point in time where the change in target engagement is greatest and where it approaches 0, meaning minimal further improvement is anticipated. Although mid-treatment scans will occur at weeks 8 and 12, we will estimate change continuously so the optimal dosage is not restricted to one of those timepoints.

**Aims 3 and 4:** To evaluate the efficacy of BATA, relative to MBCT, for treating anhedonia, functional outcomes, and behavioral indices of reward sensitivity, we will test for differential change over time between those who receive BATA and those who receive MBCT post-treatment. We will use an intent-to-treat (ITT) analysis for patients who receive BATA relative to those who don't. The ITT model will be a repeated-measures ANCOVA with effects for treatment condition (BATA, MBCT), outcome measure (SHAPS, PRT, etc), time (pre-treatment, post- treatment) and their interactions. The interaction tests will assess mean differences at each time point as well as differences in the degree of change between the groups. This also provides tests of each group relative to their baseline scores. We will include gender and age as covariates in these models. \*\*We will also note any participants who were enrolled in the study and had PRT & EffRT reward tasks data omitted during COVID-19 times.

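### Five primary endpoints are listed without ranking or any multiplicity rule; on the plan's stated alphas the family-wise false-positive rate is about 18.5% under independence

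*Combined protocol and SAP*

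**What the plan says.** The synopsis (Section 1.1, Endpoints) lists as primary the imaging measures "Tasking based activation to Monetary Incentive Delay (MID) Task; Task based activation to Emotion Reactivity task (Hammer") and the behavioural and observational measures "Probabilistic Reward Task (PRT) and EffortExpenditure for Reward Task (EEfRT); Changes in SHAPs scores pre/post treatment". That makes five, with no order among them.

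Section 9.1 has two power paragraphs:

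- The paragraph headed Aims 1, 2 and 5 calculates power for Aim 1 only, at alpha 0.025, and gives no reason for that level. It says in general terms that the aims using all 210 participants will have more power.
- The paragraph headed Aims 3 and 4 uses alpha 0.05 and covers one outcome: "Our power analysis addresses the effects of BATA versus MBCT on SHAPS scores".

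Section 9.2 analyses Aims 1 and 5 with a treatment by region by time ANCOVA followed by region-wise post-hoc comparisons. It analyses Aims 3 and 4 with a repeated-measures ANCOVA that has a factor for "outcome measure (SHAPS, PRT, etc"). Neither model comes with a test level, an order of testing or a correction. The only corrections in Section 9.2 are for exploratory work: a false discovery rate of 0.01 for whole-brain activation and a family-wise 0.05 for whole-brain connectivity.

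**The concern.** The exploratory maps are protected against multiplicity and the primary endpoints are not. CN, rACC, PRT, EEfRT and SHAPS can each yield a significant result that is truthfully reported as a primary finding, and the plan does not say which result carries the efficacy conclusion.

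The ranking also matters because the protocol treats its primaries unequally in practice. Sections 1.3, 4.2 and 10.1.10 allow the computer tasks, which produce PRT and EEfRT, to be omitted without a deviation. Section 4.1 ends new imaging enrolment with the June 2022 amendment while therapy enrolment continues. The five endpoints will therefore rest on different subsets of participants. Without a stated order, emphasis can shift after the fact to whichever endpoint succeeds.

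**Working it through.** **Inputs**

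- Five superiority tests: CN and rACC (both from the MID task), PRT, EEfRT and SHAPS. The amygdala test is left out because Section 4.1 predicts no decrease, so a significant decrease would count against the hypothesis.
- Alpha 0.05 for Aims 3 and 4, and 0.025 for the fMRI models (both Section 9.1). Sidedness is not stated; two-sided is assumed. Section 9.2 gives no level for Aim 5; 0.025 is carried over because Section 9.1 groups Aim 5 with Aims 1 and 2.
- SHAPS power inputs (Section 9.1): "With 65 subjects per treatment group with complete data at post-treatment", so N = 130; "assumed correlation between assessments of 0.35 (based on preliminary studies"); f = 0.2 and f = 0.14.
- Correlations among the endpoints are not in the documents. Values of 0.3 to 0.7 are assumed.

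**Step 1: reproduce the plan's power**

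Section 9.1 states "we will have 98% power to detect small" effects of f = 0.2, and 80% at f = 0.14. The repeated-measures within-between interaction formula is λ = f² × N × m / (1 − ρ), with m = 2 and an F test on 1 and 128 degrees of freedom.

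- f = 0.2: λ = 0.04 × 130 × 2 / 0.65 = 16.0, power 97.8%.
- f = 0.14: λ = 0.0196 × 130 × 2 / 0.65 = 7.84, power 79.4%.

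Both figures are reproduced. They apply to SHAPS tested alone at 0.05.

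**Step 2: family-wise error with no true effect, independent tests**

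Family-wise error = 1 − Π(1 − αᵢ).

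- Stated alphas (three at 0.05, two at 0.025): 1 − 0.95³ × 0.975² = 1 − 0.8574 × 0.9506 = 18.5%.
- All five at 0.05: 1 − 0.95⁵ = 22.6%.
- SHAPS, PRT and EEfRT only: 1 − 0.95³ = 14.3%.

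These count false positives in either direction. In the predicted direction only, the stated alphas give 1 − 0.975³ × 0.9875² = 1 − 0.9269 × 0.9752 = 9.6%, against 2.5% for one two-sided 0.05 test.

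**Step 3: positive correlation (simulation, equally correlated normal statistics, one million draws)**

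| Assumed correlation | Stated alphas | All at 0.05 |
|---|---|---|
| 0.3 | 17.1% | 20.9% |
| 0.5 | 15.2% | 18.3% |
| 0.7 | 12.5% | 14.9% |

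**Step 4: what control would cost SHAPS**

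- Bonferroni across five: 0.05 / 5 = 0.01 each, family-wise error 1 − 0.99⁵ = 4.9%. SHAPS power falls to 91.5% at f = 0.2 and 57.5% at f = 0.14.
- SHAPS ranked first at 0.05: power stays at 97.8% and 79.4%.

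**The case against.** **The plan is not five free-standing tests.** Section 9.2 specifies two ANCOVAs, one with region and one with outcome measure as a factor. That is true, but no omnibus test is said to gate the separate comparisons, so the structure gives no protection as written.

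**The protocol has a joint criterion.** Section 4.1 makes future larger studies conditional on BATA both engaging brain targets and reducing anhedonia, and requiring both would not inflate error. Sections 9.2 and 9.2.2 also base the R33 go/no-go decision on the ROI analysis alone. But the first statement says when further research would follow and omits PRT and EEfRT, and the second closes the R61 phase. Neither is a rule for claiming success in the full sample.

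**Ranking SHAPS above everything is a choice, and a debatable one in a target-engagement trial.** If SHAPS missed against an active comparator, Aim 5's replication of Aim 1 would lose its confirmatory test. This stands, and the recommendation keeps CN and rACC in their own family.

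**Stronger readings that the documents do not support**

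- A reader might infer that every endpoint in Aims 3 to 5 is tested at 0.05, giving an error of about 23%. Section 9.1 ties 0.05 to Aims 3 and 4 and puts Aim 5 under the heading that uses 0.025.
- A reader might add the amygdala as a sixth test, giving 1 − 0.95⁶ = 26.5%. That counts a prediction of no decrease as a chance of success.
- A reader might conclude that a chance primary finding is likely. A rate of 15 to 23% is well above 5% but is not likely.
- A reader might say that the plan has no error control at all. It has some, for exploratory imaging only.

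**Conclusion.** The concern holds: five unranked primary endpoints, no multiplicity control over them, two alphas with no stated rationale, and no test level for Aim 5 in the analysis section. The false-positive rate across the five superiority tests is about 18.5% on the stated alphas under independence, about 15% at a correlation of 0.5, and 22.6% if all are tested at 0.05 independently. For the three Aims 3 and 4 endpoints alone it is 14.3%.

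These figures assume no true effect on any endpoint, two-sided tests, the Section 9.1 power alphas carried into the tests, and one test per endpoint. The last assumption favours the plan, since Section 4.2 names no single summary score for PRT or EEfRT. The exact size depends on correlations that the documents do not give, but every scenario shown is at least 2.5 times the nominal 5%.

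**What to change.** In Sections 1.1 and 9.2, before the full-sample comparison is analysed:

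- **Aims 3 and 4.** Name SHAPS, the only endpoint of the full-sample aims with a calculated power, as the first-ranked efficacy test at two-sided 0.05. Test PRT and EEfRT with Holm only if SHAPS succeeds (first step 0.05 / 2 = 0.025). Otherwise report both as supportive, with confidence intervals.
- **Aim 5.** State that CN and rACC form a separate target-engagement family tested at 0.025 each, consistent with Section 9.1.
- **Threat task.** State that it is a specificity check reported with a confidence interval.
- **Interpretation.** State that a positive imaging result alone is not evidence of clinical efficacy.

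Each family is then held at 5%, and the two together at no more than 10%. If the sponsor wants 5% across all five tests, use SHAPS first and then Holm on the other four (first step 0.05 / 4 = 0.0125). That also makes CN and rACC depend on SHAPS.

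The cost is wording, with no new data. SHAPS loses no power. PRT and EEfRT lose some, and lose confirmatory status if SHAPS fails.

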## 1.2 SCHEMA

[figure not shown]

Figure 1: R61 Study Flow

[figure not shown]

Figure 2: R33 Study Flow

## 1.3 SCHEDULE OF ACTIVITIES (SOA)

## TIMELINE OF STUDY ASSESSMENTS AND PROCEDURES:

Assessment/Procedure	Online/Phone Screen	Remote/In Person Screen (at Duke) - can be split in 1-2 visits (part remote/part in-person)**	Pre-Tx fMRI (at UNC)	Intervention therapy sessions at Duke) 	Wks 4, 8 & 12 (if applicable) 	fMRI (wk 8 & 12) 	Study Completion Visit-Part I (Duke)	Part II Post-Tx fMRI (UNC)
Online/Phone Screen Questionnaire	X							
Informed consent		X (via Duke REDCap econsent)	X (UNC specific consent)					
SHAPS	X	X	X	X	X	X	X	X
C-SSRS		X			X (post)		X (post)	
SCID5 relevant to inclusion /exclusion, NART		X						
SCID-5-RV		X						
[name] & Background info, CGI-S, CTQ		X						
R61 Phase: BDI-II, BAI, SF-36, PhenX depression & perceived stress, PCL-5, PSWQ, IDAS, TMS, SRS-2		X			X		X	
R33 Phase: BDI-II, BAI, SF-36, PhenX depression & perceived stress, PCL-5, PSWQ, TMS, MAPS, IDS-RS, BADS		X			X		X	
R33 Phase: WAI					X		X	
EEfRT, PRT		X			X		X	
Caffeine, Nicotine, Alcohol & sleep day of intake		X	X		X	X	X	X
Urine Pregnancy Test; PEERS (female only)			X (pre)			X (pre)		X (pre)
CGI-I, % homework tasks completed				X			X	
MID			X 			X		X
fMRI			X 			X		X
MRI checklist			X			X		X
Urine Drug Screen		X**						
Acceptability Questionnaire							X	

Between 8-15 weeks of therapy sessions (therapy will be either MBCT or BATA), in-person or remote during COVID-19 guidelines.

At visits week 4, 8 & 12 (if applicable), subjects will complete EEfRT & PRT computer tasks at the beginning of the visit followed by the therapy session or if during COVID-19 times, at a separate in-person visit from the remote therapy session. All paperwork done at therapy visits will be done in addition to procedures noted in this column. They will then complete the REDCap questionnaires at these key assessment time points (either in-person or done remotely by REDCap survey invitation). If the final therapy visit is before week 8, there will be three assessment points (pre-treatment, week 4, and at the last therapy visit). If the final therapy visit is between week 8 and week 12, there will be four assessment points (pre-treatment, week 4, week 8, and at the last therapy visit). If the final therapy visit is after week 12, there will be five assessment points, and post-treatment assessments will be administered either at the last therapy session or separately if therapy was remote. COVID-19

Update: \*\*Please note that the conduct of the computer tasks with CSSRS at the in-person assessment visit, wks 4, 8, 12 and final visit are contingent upon the building availability and approval of in-person visits either at Duke or UNC. If not available and approved, the computer tasks with CSSRS will be omitted until the study team have the appropriate approvals to do the tasks at an in-person visit. These omissions (skipping the in-person visit) will not be considered protocol deviations since the omissions are necessary to be able to open the study and begin to collect the main primary outcomes of imaging and therapy.

This column is only for the first 60 subjects randomized as part of Phase I, R61. The R61 study will be entering a no-cost extension at the end of the current project period to allow for completion of data collection for this phase. Due to limited funds, the number of scans obtained is being reduced from up to 4 scans to two scans (pre- and post-treatment) for participants who are consented at UNC as of November 1.

MID practice is included & done first to determine reaction time

Includes mock scan and fMRI scan

\*\*While Duke is not open to in-person visits (COVID), this 2nd assessment visit that includes an additional CSSRS, alcohol, caffeine, sleep and 2 computer tasks, may be done at UNC. Urine drug screen would be skipped if done at UNC or there are not approvals at Duke for in-person visit and this won't be considered a protocol deviation.

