**Aims 3, 4, and 5 pertain to all 210 participants randomized (n=105 to receive BATA and n=105 to receive MBCT).**

Aim 3: We predict that BATA will produce clinically and statistically significant improvements in anhedonia and functional outcomes that exceed those due to the comparison treatment.

Aim 4: We predict that BATA will improve behavioral indices of reward sensitivity.

Aim 5: To evaluate the effects of BATA versus a comparison treatment on neural response to rewards. We predict that, consistent with Aim 1, BATA will increase right CN activation during reward anticipation and decrease rACC activation during reward outcomes and that BATA will not decrease amygdala activation to threat, confirming the specificity of BATA for targeting these positive valence neural systems. This Aim will provide a replication and extension of Aim 1 findings with a larger sample and with an optimal treatment dose.

In the PET sub-study, Hypothesis 1- BATA, but not the comparison treatment, will result in increased phasic striatal DA release but will not influence background DA striatal tone. Hypothesis 2- that normalization of fMRI-derived mesocorticolimbic activation due to BATA specifically will be associated with increased phasic DA release but no change in background DA tone during incentive processing.

This is not a pilot study but rather a Phase I/II study. The R61 phase (Phase I) of the protocol is designed to provide preliminary data for the acceptability, identification of the optimal dose of BATA as well as the preliminary efficacy of BATA in subjects with anhedonia compared to those in the MBCT control group. Using the fMRI data, this phase of the study will test if BATA produces changes in neural responses to reward anticipation and reward outcomes that exceed changes in the MBCT group and does not impact neural responses to threat. As such, a small group (N = 60) of subjects will be in this blinded phase and they will complete up to a total of 4 fMRI scans (pre-treatment, week 8, 12 and post-treatment). The R61 study will be entering a no-cost extension at the end of the current project period to allow for completion of data collection for this phase. Due to limited funds, the number of scans obtained is being reduced from up to 4 scans to two scans (pre- and post-treatment.) for participants

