Duke: At the final therapy visit (anytime between 8-15 weeks as determined by Duke/UNC study team) or separately, the subject will be asked to redo the computer tasks (EEfRT and PRT), complete the SHAPS & % homework tasks 1 last time and then again be asked to complete most of the online questionnaires they completed at the screening assessment visit ((i.e. R61: the PSWQ, PCL-5, BDI-II, BAI, IDAS, SF-36, TMS, SRS-2, PhenX measures of related to depressed mood and perceived stress, R33: the MAPS, IDS-RS measures related to anhedonia, BADS, WAI, PSWQ, PCL-5, BDI-II, BAI, SF-36, TMS, and PhenX measures of related to depressed mood and perceived stress). They will complete them directly in REDCap. Next, the C-SSRS will be done and the subject will be asked a series of questions about feasibility and acceptability of procedures (exit interview), and will be offered referrals for other mental health services as needed. Finally, they will be scheduled for their final fMRI brain scan at UNC. Note: Especially during COVID-19, the final computer tasks, CSSRS, exit interview, and caffeine/alcohol questions may be done at UNC and survey invitation sent out for the REDCap questionnaires. **\*\*Please note that the conduct of the computer tasks with CSSRS at the in-person final visit are contingent upon the building/room availability and approval of in-person visits either at Duke or UNC. If not available and approved, the computer tasks with CSSRS will be omitted until the study team have the appropriate approvals to do the tasks at an in-person visit. These omissions (skipping the in-person visit) will not be considered protocol deviations since the omissions are necessary to be able to open the study and begin to collect the main primary outcomes of imaging and therapy. If omitted, the participant will be emailed the REDCap survey invitation to complete only the self-report with exit interview, as applicable.**

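### PRT and EEfRT are primary endpoints that may be omitted at baseline and follow-up, but the Aims 3 and 4 analysis has no method for the resulting gaps and the only power figures are for SHAPS

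*Combined protocol and SAP*

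**What the plan says.** The Synopsis (Section 1.1) states that "All participants will complete interview, symptom, and behavioral measures before and after treatment". Its primary endpoints include, besides the two imaging tasks, "Probabilistic Reward Task (PRT) and EffortExpenditure for Reward Task (EEfRT); Changes in SHAPs scores pre/post treatment". Section 4.1 adds that "Aims 3, 4, and 5 pertain to all 210 participants randomized", and Aim 4 concerns behavioral indices of reward sensitivity.

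The COVID-19 update to footnote 2 of Section 1.3 reads: "conduct of the computer tasks with CSSRS at the in-person assessment visit, wks 4, 8, 12 and final visit are contingent upon the building availability". It also requires approval at either site. Failing that, "the computer tasks with CSSRS will be omitted until the study team have the appropriate approvals to do the tasks at an in-person visit". Such omissions are not deviations. The reason given is that the study can then open and begin collecting imaging and therapy, which the text calls its main primary outcomes. The rule recurs in Section 4.2 and Section 10.1.10. UNC is a fallback site: at the end of treatment "the final computer tasks, CSSRS, exit interview, and caffeine/alcohol questions may be done at UNC", and Section 1.3 says the same of the baseline tasks.

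Section 9.1 gives one power calculation headed Aims 3 and 4, computed for SHAPS. "With 65 subjects per treatment group with complete data at post-treatment", alpha .05 and a correlation of 0.35, it reports 98% power at f = .2 and 80% at f = .14.

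Section 9.2 gives one repeated-measures ANCOVA for Aims 3 and 4, described as intent-to-treat. Its factors are treatment, outcome measure (SHAPS, PRT and others) and time, and time has two levels, pre and post. On the missing tasks it says only: "We will also note any participants who were enrolled in the study and had PRT & EffRT reward tasks data omitted during COVID-19 times".

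**The concern.** A baseline task that is omitted cannot be recovered once therapy has started. The plan therefore expects some participants to have a post-treatment PRT or EEfRT reading and no baseline, and others to have neither. It does not say how either group enters the analysis.

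Two consequences follow if the named model is fitted by complete cases. A post-only participant carries no weight in the group-by-time test, although the reading is informative about the arm difference. And because outcome measure is a factor in the same model, listwise deletion could remove a participant's SHAPS values because the task values are absent. SHAPS is completed at therapy sessions, including remote ones, so it continues when the tasks do not.

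The record of the gaps is also uneven. Section 7.3 documents a task visit skipped for sickness, weather or travel as a deviation, while the COVID-19 rule treats the same missing primary datum as no deviation. Completeness matters more for the latest participants. Sections 4.1 and 4.2 end new UNC imaging enrolment with the June 2022 amendment, so SHAPS and the two tasks are the only listed primary endpoints still collected for them.

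**Working it through.** **1. Reproducing the plan's power.** Inputs from Section 9.1: 65 per arm (N = 130), alpha .05, r = .35, two groups, two times. For a repeated-measures within-between interaction, lambda = f² × N × 2 / (1 − r), tested against F(1, N − 2).

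- f = .2: lambda = .04 × 130 × 2 / .65 = 16.0; power 97.8% (stated 98%).
- f = .14: lambda = .0196 × 130 × 2 / .65 = 7.84; power 79.4% (stated 80%).

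Both reproduce. They describe 130 complete pre/post pairs on SHAPS. No effect size, correlation or power is given for PRT or EEfRT.

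**2. The same formula by number of complete task pairs**, borrowing r = .35 and f from SHAPS:

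| Pairs per arm | Lambda at f = .14 | Power at f = .14 | f detectable at 80% |
|---|---|---|---|
| 65 | 7.84 | 79% | .141 |
| 58 | 7.00 | 75% | .150 |
| 52 | 6.27 | 70% | .158 |
| 46 | 5.55 | 64% | .168 |
| 39 | 4.70 | 57% | .183 |

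**3. How much omission it takes to get below 65 pairs.** The 65 per arm already allows 210 − 130 = 80 participants (38%) to lack complete data. Section 5.4 gives 81% retention, stated for imaging sessions and assumed here for the tasks: 105 × .81 ≈ 85 per arm. Since 65/85 = .765, the stated figures hold until about 24% of completers lack a task pair.

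- 10% omitted: about 76 per arm; power at f = .14 is 85%.
- 20% omitted: 68 per arm; power is 81%.

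If all omissions fall among the 150 R33 participants, break-even is about 40 lost pairs of 150 × .81 ≈ 122 (33%). With the roughly 90% post-treatment participation quoted under Aims 1 and 5, it is 59 of 135 (44%).

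**4. What post-only readings are worth.** Let q be the share of participants with a post reading who lack a baseline. Assume equal SDs, r = .35 and a baseline mean common to the arms. Relative to one participant with a post reading only, a complete pair carries information 1/(1 − r²) = 1/.8775 about the post-treatment arm difference. The variance ratio, keeping versus dropping post-only participants, is

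[(1 − q)/.8775] / [(1 − q)/.8775 + q].

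- q = .10: 1.0256/1.1256 = .911, a 9% reduction.
- q = .20: .9117/1.1117 = .820, an 18% reduction.
- q = .30: .7977/1.0977 = .727, a 27% reduction.

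The values of q are assumed; the documents give none.

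**The case against.** The strongest reply is that the power claim for Aim 4 is not shown to fail. A reader might infer that Aim 4 lacks the stated power. The documents do not support that: the figures rest on 130 complete pairs, not 210, no omission count is given, and step 3 shows that 10% or 20% omission among 85 completers per arm leaves at least 80% power at f = .14. This part of the objection stands in full.

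A reader might also infer that the plan discards post-only readings. Section 9.2 states no deletion rule and calls the analysis intent-to-treat, and a likelihood-based fit would keep them. The loss follows from the usual way of fitting the named model, so the defect is that the method is unspecified.

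Nor does the reference to all 210 misstate anything. It describes the randomised population for the aim, and completeness is handled separately in Section 9.1. It should not be narrowed to those with task data.

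Finally, a reader might conclude that the gaps were simply avoidable by running the tasks at UNC scan visits. The plan already allows UNC as a fallback, makes omission temporary and subject to approval at either site, and since June 2022 confines the tasks to Duke with no new UNC imaging. That instruction would repeat existing text for earlier participants and conflict with current text for later ones.

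The wording that ranks imaging and therapy first may be meant as a priority for reopening and not as a demotion of the tasks. Even so, the text does not say so.

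**Conclusion.** The point holds as a gap in the analysis plan. Two listed primary endpoints may be missing by rule at baseline and follow-up, the model named for them has no missing-data method, and the only power figures under the Aim 4 heading belong to SHAPS.

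The gain from keeping post-only participants is a variance reduction of about 9 to 27% for 10 to 30% missing baselines, given r = .35, equal SDs and a likelihood analysis whose missingness assumption is reasonable. Omission tied to building approval makes that assumption plausible and makes arm bias a lesser worry than precision. Aim 4's power is undetermined: it matches the stated figures only with about 130 complete pairs and the SHAPS values of f and r, and at f = .14 it would be 75, 70, 64 or 57% at 58, 52, 46 or 39 pairs per arm.

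**What to change.** 1. **Section 9.2, Aims 3 and 4.** Replace the single model with separate models for SHAPS, PRT and EEfRT. In each, treat the pre and post values as responses in a likelihood-based repeated-measures model with one baseline mean common to the randomised arms, keeping gender and age as covariates. Include every randomised participant with at least one reading, and state the missing-data assumption.
2. **Section 9.1.** Label the 98% and 80% figures as SHAPS only. State that Aim 4's power depends on the number of complete task pairs, and give the detectable effect at the number obtained.
3. **Section 1.3 footnote 2 and its repeats in Sections 4.2 and 10.1.10.** Record each omitted PRT or EEfRT as missing primary-endpoint data, and report the counts by visit and arm. Reconcile the phrase that ranks imaging and therapy as the main primary outcomes with the endpoint list in Section 1.1.

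The cost is some rewording and a possibly less favourable stated power for Aim 4. No new data or visits are needed.
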